7.6.2 Laboratory Assessments

Descriptive statistics for quantitive laboratory parameters at each time point and change from baseline will be provided by group.

Shift tables from baseline to the worst intensity grade will be provided by group for each gradable laboratory parameter, where low/normal/high or abnormal not clinically significant/ abnormal clinically significant /normal status had been ascertained.

Also, shift tables from baseline to the worst laboratory abnormality grade will be provided by group for each gradable laboratory parameter (if applicable), where laboratory abnormality grade is calculated according to the Appendix C Table 4: *Laboratory abnormality grading scale*.

Additionally, the occurrence of clinically significant abnormal laboratory results will be provided for each parameter and visit by group.

All of laboratory assessments will be listed by subject along with the normal ranges. Values that are below or above the normal ranges will be flagged.

7.6.3 Vital Signs

Descriptive statistics for each vital sign parameters at each time point and change from baseline will be provided by group.

All of vital sign data will be listed by subject.

7.6.4 Physical Examination

Shift tables from baseline to the worst intensity grade will be provided by group for each gradable physical examination parameter, where normal/abnormal not clinically significant/ abnormal clinically significant status had been ascertained.

All of physical examination will be listed by subject. Abnormal not clinically significant/ abnormal clinically significant status will be flagged.

7.7 Multiplicity

No multiplicity adjustment will be implemented in this Phase I dose-exploratory study.

7.8 Subgroup Analyses

In addition to the analyses on pooled adult and elderly population, immunogenicity, exploratory and safety analyses will be conducted separately on adult subjects and elderly subjects, respectively.

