#### **Trial Design:**

This is a phase I, randomized, placebo-controlled, observer-blind, safety and immunogenicity study of SARS-CoV-2 mRNA vaccine (BNT162b1) in Chinese healthy subjects. After randomization, the trial for each subject will last for approximately 12 months. Screening period is 2 weeks prior to randomization (Day -14 to Day 0), and each dose of either SARS-CoV-2 vaccine (BNT162b1) or placebo will be given intramuscularly (IM) on Day 1 and on Day 22. After each age group completes the follow-up 28 days after boost vaccination (Day 50), initial analysis will be conducted.

Subjects who are  $\ge$ 18 years old and  $\le$  55 years old will be enrolled in adult group, and healthy elderly subjects who are  $\ge$ 65 years old and  $\le$ 85 years old will be enrolled in elderly group. Approximately 72 subjects for each age group will be allocated to three cohorts (BNT162b1 high-, low-dose groups and placebo group) in parallel, with approximately 24 subjects at each BNT162b1 dose level, including 24 placebo group subjects, the subjects will be randomized in a 1:1:1 ratio.

After the 14-day safety observation post the prime vaccination of the subjects in adult group, the prime vaccination for the subjects in the elderly group will start. SRC will review the available safety and tolerability data of all subjects in a cohort (including safety observation 14 days after the prime vaccination for all subjects in this cohort) before starting the boost vaccination for each cohort, to decide whether the BNT162b1 vaccine can be boosted.

For dose allocation design, see schematic diagram in **Figure 1**. For the planned assessments and visits, see schedule of activities in **Table 2**.

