#### **Independent Data Monitoring Committee:**

The study will be overseen by an Independent Data Monitoring Committee (IDMC). IDMC will consist of 3 or 5 independent members (including epidemiologist, clinical experts, and statistical expert) and 1 independent non-voting statistician.

The IDMC is required to review the unblinded data when a significant event or risk that could cause the study to be suspended occurs. Based on the results of the safety data review, IDMC can request the suspension of investigation in a certain dose group/age group, or suspension of boost vaccination, and can also provide recommendations for subsequent development based on the periodical study data. This study will proceed in accordance with the protocol-specified procedures if no IDMC recommendation for suspension or modification is received.

The IDMC meetings will consist of open and closed face-to-face meetings or teleconference calls. The type and frequency of scheduled meetings will depend on the subject enrollment and safety event rates. Unscheduled ad hoc meetings will occur if a stopping rule occurs, or at any time consultation is requested by the Pharmacovigilance Study Team.

The IDMC will review safety data on an ongoing basis, when the reported AEs meet with the dose-limiting toxicity (DLT) criteria, the IDMC will review all relevant safety data and consider a possible pause of the study, if it deems necessary:

See IDMC charter for more information. The IDMC will act according to written procedures described in IDMC charter.

BNT162-03 Version 3.0 (5 AUG 2020)

Table 2 Schedule of activities

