#### 13.1.5 Immunogenicity analysis

Descriptive statistics for the primary and secondary immunogenicity endpoints, including estimates and 95% confidence intervals (95% CI) for GMT and SCR, will be provided by time point and by different age groups, different dose cohort of BNT162b1 and placebo group).

Different BNT162b1 dose cohorts will be compared in pairs, and the GMT ratio of each two dose cohorts as well as the point estimate value of SCR difference and 95% CI will be calculated. Generally, immunogenicity will be summarized and analyzed based on age groups and dose cohorts.

- *Seronegative subjects*: Subjects with no detectable serum antibodies (test results are lower than the lower limit of detection) as measured by ELISA/neutralization assay.
- *Seroconverted subjects*: The serum antibody titer after vaccination of subject is at least 4 times higher than baseline by ELISA/neutralization assay.

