7.1.1 General Analysis Method

Descriptive Statistics

Unless otherwise specified, the following descriptive statistics will be provided according to the type of variable:

- ✓ Continuous variables will be summarized by mean, standard deviation (SD), median, minimum (min) and maximum (max).
- ✓ Category or ordinal variables will be summarried by the number and percentage, where the percentage will be calculated based on the number of subjects in the corresponding analysis set as denominator and may be presented with exact 95% Clopper-Pearson CIs.

Additionally, descriptive statistics of titer and fold increase of titer will include geometric mean and its two-sided 95% confidence interval (CI). The geometric mean titer (GMT) is calculated as the mean of the logarithm of the functional antibody titers, back-transformed into the original scale. Two-sided CIs will be obtained by calculating CIs using Student's t-distribution for the mean of the logarithmically transformed assay results and transforming the limits back to the original scale.

Geometric mean fold rise (GMFR) is calculated as the mean of the difference of logarithmically transformed assay results (post vaccination time point – pre vaccination time point) and back-transformed into the original scale. Two-sided CIs will be obtained by calculating CIs using Student's t-distribution for the mean difference of the logarithmically transformed assay results and transforming the limits back to the original scale.

Decimal Places

Unless otherwise specified, the decimal places will follow the following rules:

- \checkmark The decimal places of min, max, median, Q1 and Q3 are consistent with the original data.
- ✓ The decimal places of mean, GM, SD and 95% CI are 1 more than the original data.
- ✓ Keep 2 decimal places in the percentage.

- ✓ Keep 2 decimal places in coefficient of variation (CV) and geometric coefficient of variation (GCV).
- ✓ Keep 4 decimal places if the p value is no less than 0.0001, and present as "<0.0001" if the p value is less than 0.0001.

- ✓ Keep 3 decimal places for all testing statistics.
- ✓ Keep 2 decimal places for the derived data.

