7.1.5 Tables and listings

> Tables

In general, data will be summarized by group (i.e., low dose, high dose and placebo). The groups will be presented in columns.

> Listings

Unless otherwise specified, dose level and subject number will always be included in listings. The EDC original data will be displayed in priority. All listings will be sorted first by dose level, then by subject number and finally, if applicable, by visit number and/or a relevant date (e.g. date of onset of AE).

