7.4 Immunogenicity Analyses

Descriptive statistics, including geometric mean and 95% confidence intervals (CIs), for GMT and GMFI of anti-S1 IgG antibody at all post-baseline time points will be presented by group.

The number and percentage of subjects with seroconversion of anti-S1 IgG antibody will be summarized by group for all post-baseline time points. The 95 % confidence interval of percentage will be calculated by Clopper-Pearson method.

The geometric mean of anti-S1 IgG antibody at each time points will be plotted in log-scale. The reverse cumulative distribution plot is to display S1 IgG antibody distribution at each time points by group.

The same statistical methods as anti-S1 IgG antibody and seroconversion rate will be conducted to analyze anti-RBD IgG antibody and SARS-CoV-2 neutralizing antibody (based on true virus' SARS-CoV-2 neutralizing test).

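### The pooled adult-plus-elderly summary in SAP 7.8 has no age-stratified method, so its intervals over-cover if titres differ by age, and its Month 3 value comes from adults only

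*SAP*

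**What the plan says.** **SAP.** Section 7.8, headed as subgroup analyses, states: "In addition to the analyses on pooled adult and elderly population, immunogenicity, exploratory and safety analyses will be conducted separately", that is, once for each age group. Section 7.1.5 sets the default columns: "In general, data will be summarized by group (i.e., low dose, high dose and placebo"). Section 7.1.1 gives the GMT interval: "Two-sided CIs will be obtained by calculating CIs using Student's t-distribution for the mean of the logarithmically transformed assay results", and builds the fold-rise interval in the same way. Section 7.4 adds for seroconversion: "The 95 % confidence interval of percentage will be calculated by Clopper-Pearson method". None of these sections has an age stratum, weight or model term. Section 2.3 declares the SAP's analyses consistent with the protocol.

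**Protocol.** The Trial Design part of the summary says: "Approximately 72 subjects for each age group will be allocated to three cohorts", at 1:1:1 with about 24 per arm. The elderly group opens only after 14 days of adult safety observation (6.1, 6.2). Section 13.1.5 says: "Generally, immunogenicity will be summarized and analyzed based on age groups and dose cohorts", and 13.1.6 closes by giving the safety summary by age group and dose cohort. Section 13.1.2 lets groups be merged where appropriate and gives no method for doing so.

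**Sampling.** Protocol 9.1.6 and Table 2 schedule adult antibody samples at Visits 1, 5, 6, 8, 10, 11 and 12. The elderly have the same visits except Visit 10, which is Month 3. SAP 5.1 nevertheless lists GMT, GMFI and SCR at Month 3 without distinguishing age, and SAP 6 analyses Month 3 persistence in evaluable TVC subjects.

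**Suspension.** The protocol's summary (and 11.2) provides that the "IDMC can request the suspension of investigation in a certain dose group/age group, or suspension of boost vaccination".

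**The concern.** Age group is a design factor here. The two groups have their own enrolment targets, entry criteria and start times, and the 24/24 split within each arm is fixed in advance. A one-sample interval on the 48 treats that fixed split as random variation. Any adult/elderly difference then enters the SD and widens the interval for a reason unrelated to sampling error.

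Pooling also keeps columns and time points comparable only while both age groups contribute equally. Where one is absent, the pooled geometric mean changes because the age mix changes. SAP 7.4 plots geometric means at each time point, and durability of the response is a secondary objective. A Month 3 point that is adult-only, standing between mixed-age points at Day 43 and Month 6, could be read as a feature of the immune response.

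**Working it through.** **1. The plan's own figure.** Protocol 13.3 and SAP 4.3 state an 86.5% chance of at least one TEAE in 24 subjects at a rate of 8%. Check: 1 − 0.92^24 = 0.865, which reproduces. The figure belongs to one dose-by-age cell of 24. For a pooled column of 48 it would be 1 − 0.92^48 = 0.982. The design was therefore sized on the cell.

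**2. Interval width for GMT.** Inputs are 24 adults and 24 elderly per arm (from the documents), within-age SD of ln titre σ, and adult/elderly GMT ratio r. The documents give neither σ nor r, so both are assumptions shown as ranges.

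With d = ln r, each subject's age-group mean lies d/2 from the pooled mean. The between-age sum of squares is 48·(d/2)² = 12d², so the expected one-sample variance is σ² + 12d²/47, close to σ²·[1 + d²/(4σ²)]. The age-stratified variance is σ². The half-width ratio is therefore √(1 + (ln r)²/(4σ²)).

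| r | (ln r)² | σ = 1.0 | σ = 0.8 | Widening |
|---|---|---|---|---|
| 1 | 0 | 1.000 | 1.000 | 0% |
| 1.5 | 0.164 | √1.041 = 1.020 | √1.064 = 1.032 | 2-3% |
| 2 | 0.480 | √1.120 = 1.058 | √1.188 = 1.090 | 6-9% |
| 3 | 1.207 | √1.302 = 1.141 | √1.471 = 1.213 | 14-21% |

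Simulation with 20,000 replicates gave coverage of the nominal 95% pooled interval of 96.2-96.7% at r = 2 and 97.5-98.2% at r = 3. The stratified interval covered 94.9-95.1%. A second simulation over a wider SD range (0.3 to 0.6 on the log10 scale) gave widening of 1-4%, 3-12% and 8-28% at r = 1.5, 2 and 3.

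The same formula serves GMFI, with σ and r read as the SD and age ratio of the fold rise.

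**3. Seroconversion rates.** Compare the pooled variance p̄(1 − p̄)/48 with the stratified variance [p_A(1 − p_A) + p_E(1 − p_E)]/96. The rates are illustrative.

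- 100% vs 80%: 0.09/48 = 0.001875 against 0.16/96 = 0.001667. SE ratio √1.125 = 1.06.
- 80% vs 40%: 0.24/48 = 0.00500 against 0.40/96 = 0.00417. SE ratio √1.20 = 1.10.
- Equal rates: 1.00.

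**4. An absent age group.** The age-balanced log mean is (μ_A + μ_E)/2. With adults only it is μ_A. The difference is d/2, so the geometric mean is off by a factor of √r: 1.00, 1.22, 1.41 and 1.73 at r = 1, 1.5, 2 and 3.

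- *Month 3, already scheduled.* All three pooled columns become adult-only and fall from 48 to 24 subjects. With r = 2 at that visit, an active-arm column is shifted by 1.41 against the age-balanced value.
- *One dose-by-age cell suspended, conditional.* If one elderly dose cell supplied no post-boost data, that column would be adult-only and the other mixed. Side by side they would differ by √r with no true dose effect. With all cells at 24 the shift is zero.

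**The case against.** The case against is substantial, and most of it stands as a limit on size.

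- **By-age results are already planned.** The same SAP sentence provides separate adult and elderly analyses. A reader might infer that the protocol's by-age reporting is lost or its intervals spoiled. Neither is so.
- **Merging is allowed.** Protocol 13.1.2 permits it, so a pooled summary is not in itself a departure. The permission supplies no method, however, and that gap is the point here.
- **Prominence is inferred.** A reader might conclude that the lead tables are pooled. Sections 7.1.5 and 7.8 suggest this, but the table shells are a separate attachment, and SAP 4.1 times the initial analysis by age group.
- **No age effect on titres is documented.** The protocol's background says reactions were slightly less in the elderly. That concerns reactogenicity and cannot be carried over to antibody titres. At r = 1 the intervals are correct.
- **The error is conservative and drives no decision.** SAP 7.1 plans no formal testing.
- **Dose contrasts.** A reader might infer that the planned dose comparisons are confounded with age. SAP 7.4 defines no dose contrast. The pairwise GMT ratios and SCR differences are in protocol 13.1.5, beside the statement that analysis is by age group. Confounding would need those ratios to be run on pooled data and a cell to be missing or unbalanced.

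One could also argue that the one-sample interval suits a mixed-age population. The trial samples no such population: it excludes ages between 55 and 65, and the half-and-half split was set by the design.

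**Conclusion.** The point holds in a limited form. The pooled summary is specified without regard to the factor that structures the allocation. Its intervals are too wide whenever titres differ by age: 2-3%, 6-9% and 14-21% at age ratios of 1.5, 2 and 3 under the assumed ln SD of 0.8 to 1.0, and not at all at a ratio of 1. These sizes are conditional, because the documents quantify neither input. It would go too far to say that the pooled error bars are known to be wrong.

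The firmer part is Month 3. On the protocol's own schedule the pooled GMT, GMFI and SCR there are adult-only, whatever happens to recruitment or suspension. How far this moves the GMT again depends on the unknown age ratio (√r). The suspension scenario is a contingency and affects side-by-side pooled columns, or the protocol's pairwise ratios only if they are run on pooled data.

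The separate adult and elderly results are untouched. This is a worthwhile, nearly free improvement and does not threaten the trial's conclusions.

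**What to change.** 1. In SAP 7.1.5 and 7.8, make the by-age tables the main presentation, in line with protocol 13.1.5 and 13.1.6, and move them out from under the subgroup heading.
2. Where a pooled GMT or GMFI is kept, use the equal-weight mean of the two age-group log means, (m_A + m_E)/2. Its standard error is (s_w/2)·√(1/n_A + 1/n_E), where s_w is the pooled within-age SD, with t on n − 2 degrees of freedom (46 when both cells hold 24). Back-transform the limits.
3. For pooled percentages, use an age-stratified interval, chosen so that it still behaves when a cell is at or near 0% or 100%.
4. Show a pooled figure only for time points and doses where both age groups contribute data. Label Month 3 antibody results as adult-only and leave that point off any pooled time course.
5. If pooled tables remain the main presentation, record this in SAP 2.3 as a change from the protocol.

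The cost is SAP wording and minor programming. No new data are needed and no information is lost.

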7.9 Handling of Missing Data

This study is Phase I dose-exploratory study, therefore the missing data in this study will not be handled.

7.10Timing of Statistics Analyses

Prime analyses will be conduct based on all available safety and immunogenicity data when all subjects in each age group complete Visit 9 (Day 50, 28 days after boost vaccination). Update analyses will be conduct when all subjects in each age group complete Visit 11 (Month 6 after prime immunization), Visit 12 (Month 12 after prime immunization).

Unblinding will be conduct along with the prime analysis of immunogenicity and safety at 28 days after boost immunization, but the subjects will be kept blinded.

Version History

Version	Date	Author	Changes & Rationale
V1.0	2020-08-28		Initial version.
V1.1	2020-10-29		Add laboratory analysis according to the Appendix C Table 4: Laboratory abnormality grading scale
